11.3.2.2 Analysis of North Star Ambulatory Assessment (NSAA)

Another primary objective is to evaluate the efficacy of WVE-210201 by assessing changes in the NSAA. Therefore, the primary efficacy endpoint for the EU and Japan and the key secondary endpoint for the United States and Other regions is the change in NSAA from baseline over 48 weeks. The treatment policy estimand which assesses the effect of treatment initially assigned at baseline (regardless of adherence to the planned course of treatment) will be used. The analysis population will be the ITT population. The main estimator will be a Bayesian progression model (BPM) to compare the change in NSAA between patients treated with WVE-210201 and placebo treated patients^{59,60}. The placebo data from this study will be augmented with historical control data via a Bayesian meta-analytic approach.

The BPM assumes a non-parametric rate of progression of the NSAA for placebo patients and a proportional rate of slowing NSAA progression for the treated patients relative to the placebo patients at each time point. The model will include covariate effects to measure differences in the rates of progression based on patient-specific baseline covariates. Additionally, random patient variability will be accounted for using patient-level random effects of the rate of NSAA progression. Borrowing from historical control data to augment the placebo arm information will entail including a random data source effect to model the between-source variability in NSAA progression rates.

The NSAA analysis will be independent of the dystrophin analysis described in [Section 11.3.2.1](#). Let the NSAA at visit j for patient i be Y_{ij} , for $j = 0, \dots, 4$ and $i = 1, \dots, n$. The Y_{i0} observation corresponds to the baseline visit. Visits $j = 1, 2, 3, 4$ refer to the post-baseline visits (each separated by 12 weeks). Let X_i be a vector of dimension C of baseline covariates for patient i that have been standardized. The DPM is

$$Y_{ij} = \gamma_i + \exp(\theta_{t(i)} + \eta_i + \alpha X_i + \delta_{s(i)}) \sum_{k=0:j} \beta_k + \epsilon_{ij}; \\ \epsilon_{ij} \sim N(0, \sigma_{t(i),s(i)}^2).$$

Patient-specific random effects, $\gamma_i, i = 1, \dots, n$, represent the patient-specific mean NSAA at the time of randomization.

It is assumed that $\beta_0 = 0$ and the decline in NSAA per each 12-week period for a placebo patient in this study with average baseline covariates is modelled as $\beta_k, k = 1, \dots, 4$, with the sum of all β_k equal to the total decline over 48 weeks. Each β_k is assumed to be less than or equal to zero to ensure a monotonic decline.

For patient i , the treatment arm is labelled $t(i)$ with 0 for placebo, 1 for WVE-210201 3 mg/kg and 2 for WVE-210201 4.5 mg/kg. The disease rate ratio (DRR) for treatment T is the parameter $\exp(\theta_T), T = 0, 1, 2$. For a placebo-treated patient, the DRR is assumed to be 1 ($\theta_0 = 0$). Thus, the DRR parameter for treatment T represents the multiplicative change to the mean decline of a placebo-treated patient. If the DRR is less than 1, the rate of decline for treatment T is slower than placebo; the DRR value represents the proportional slowing of NSAA progression. For example, a DRR = 0.75 corresponds to a 25% slowing in the rate of NSAA progression. The WVE-210201 treatment arms will be pooled for the NSAA analysis and the restriction that $\theta_1 = \theta_2$ incorporated into the DPM. However, if the randomization to the WVE-210201 3 mg/kg arm is stopped after an interim analysis (Section 11.5), the WVE-210201 treatment arms will not be pooled. Summaries of the posterior distribution for the DRR ($\exp(\theta_T)$) for each arm will be provided including the probability that each treatment is superior to placebo, $Pr(\exp(\theta_T) < 1)$, as well the mean and 95% credible intervals for each DRR.

Patient-specific multiplicative random effects in the slope, $\exp(\eta_i), i = 1, \dots, n$, represent the patient-specific proportional increase or decrease in the rate of progression. Covariate effects are modelled as $\alpha_c, c = 1, \dots, C$, and account for explained variability in the rate of NSAA progression due to subject-specific baseline covariates.

Random data source effects to account for the between-source variability in NSAA progression rates are modelled as $\delta_{s(i)}$, where the source of each patient is labelled $s(i)$ with 0 for this study and 1:S for the historical data sources. These source effects account for the variability in the rate of progression of NSAA between placebo and historical controls in the different data sources that are not explained by baseline covariates. For a patient randomized in this study, the source effect is assumed to be 1 ($\delta_0 = 0$).

The residual errors for the individual observations, $\epsilon_{ij}, i = 1, \dots, n$ and $j = 0, \dots, 4$, are modelled as independent normal distributions with a treatment arm and source-specific standard deviation of $\sigma_{t(i),s(i)}$.

Missing NSAA data can result from intercurrent events which include discontinuation of the study and loss of ability to complete any NSAA activities. With the selected primary estimand, missing NSAA assessments or NSAA assessments collected after randomized therapy discontinuation will be imputed using a control-based imputation strategy for treated patients. Placebo patients will have missing observations imputed assuming MAR. The loss of the ability

to complete any NSAA activities will be recorded as 0 on the case report forms and used in the analysis.

The posterior probability that the DRR is less than 1 will be assessed to determine significance of the WVE-210201 NSAA treatment effect. Superiority on slowing the rate of decline on NSAA will be declared if the posterior probability that either 1) the pooled WVE-210201 treatment effect ($\theta_1 = \theta_2$; if the low dose has not been dropped) or 2) the WVE-210201 treatment effect θ_2 (if randomization to the WVE-210201 3 mg/kg has been stopped) is superior to placebo and slows the rate of NSAA progression is greater than 0.975:

$$\Pr(\exp(\theta_2) < 1) > 0.975.$$

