11.3.3 Multiplicity considerations

The overall type I family-wise error rate for the primary and key secondary efficacy endpoint comparisons will be controlled at the one-sided, 2.5% error rate.

In the United States/Other regions, the dystrophin and NSAA efficacy analyses will be conducted as described in [Section 11.3.2](#). Simulations have demonstrated that the type I error rate is maintained across a range of parameterizations.

In the EU/Japan, the NSAA endpoint will be compared first and if the efficacy threshold is crossed, the dystrophin endpoint will be compared.

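### The NSAA model fixes this trial's source effect at zero while only the historical source effects are random; under the usual zero-mean reading this over-weights the historical controls, and the 2.5% error rate is not shown to hold under between-source drift

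*Combined protocol and SAP*

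**What the plan says.** Section 11.3.2.2 states the aim: "The placebo data from this study will be augmented with historical control data via a Bayesian meta-analytic approach". The mechanism follows: "Borrowing from historical control data to augment the placebo arm information will entail including a random data source effect to model the between-source variability". The source label runs "with 0 for this study and 1:S for the historical data sources", and the 12-week declines beta_k are defined "for a placebo patient in this study with average baseline covariates is modelled as" beta_k. This trial is therefore the reference source, with delta_0 = 0: "For a patient randomized in this study, the source effect is assumed to be 1". The 1 is the multiplier exp(0), so that sentence agrees with delta_0 = 0.

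The section gives no mean, variance, correlation or hyperprior for the historical effects. It also gives no number or size of sources and no cap on borrowing. Success is a posterior probability above 0.975 that the disease rate ratio (DRR) is below 1, with the two doses pooled unless the 3 mg/kg arm is stopped.

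Section 11.3.3 says that the family-wise error rate for the primary and key secondary comparisons "will be controlled at the one-sided, 2.5% error rate". In the paragraph on the United States and other regions it adds: "Simulations have demonstrated that the type I error rate is maintained across a range of parameterizations". No scenarios or results are listed.

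**The concern.** In a meta-analytic model the current trial is normally one more draw from the population of sources. Here its effect is a constant and only the historical effects vary. With independent zero-mean effects, each historical source becomes an unbiased reading of this trial's own placebo rate, and any feature that separates the trial from all of the sources is assumed to average out. If the trial's boys happen to decline more slowly than the historical boys, for reasons the baseline covariates do not capture, part of that gap can be read as a drug effect.

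NSAA is the primary endpoint for EU/Japan and the key secondary endpoint elsewhere. In EU/Japan a success on NSAA also opens the dystrophin test. The historical data enter the interim predictive probability that can end enrolment (Section 4.1.2), and the other secondary endpoints use an analogous model (Section 11.3.2.3).

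**Working it through.** **Inputs from the plan (Section 11.1).** SD of change 4.5; average one-year decline 3 points; 150 patients at 1:1:2:2, so 50 placebo and 100 active; 10% dropout, leaving 45 and 90.

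**Assumed, because the text gives none.** S = 2, 3 or 5 historical sources, 75 boys each; between-source SD tau = 0.1 to 0.4 on the log-rate scale (0.3 to 1.2 points on a 3-point decline); independent zero-mean source effects.

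**The plan's own figure.** For 45 v 45 (one dose against pooled placebo), SE = 4.5 × sqrt(2/45) = 0.949 and 3/0.949 = 3.16. Power is 88.5% by the normal approximation and 87.9% by noncentral t, which matches the stated 88%. No historical data enter it.

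**Variances on the log-rate scale.** (4.5/3)² = 2.25.
- Trial placebo: v0 = 2.25/45 = 0.050
- Pooled active: va = 2.25/90 = 0.025
- One historical source: vh = 2.25/75 = 0.030

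**Variance with which the historical mean informs the trial's placebo rate.**
- delta_0 fixed: qA = (tau² + vh)/S
- Exchangeable: qB = qA + tau²

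With very large sources these become tau²/S and tau²(1 + 1/S). The first goes to zero as S rises; the second cannot fall below tau².

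**Worked case, S = 3, tau = 0.2.**
- qA = (0.04 + 0.03)/3 = 0.0233; qB = 0.0633
- Placebo-equivalents, 2.25/q: 96 fixed v 36 exchangeable; the trial itself has 45
- Weight on history under the fixed model: w = 0.050/(0.050 + 0.0233) = 0.682
- Variance the fixed model claims: 0.025 + 1/(1/0.0233 + 1/0.050) = 0.0409
- Variance if the trial is a draw from the same sources: 0.025 + 0.682² × 0.0633 + 0.318² × 0.050 = 0.0595
- One-sided error: P(Z > 1.96 × sqrt(0.0409/0.0595)) = P(Z > 1.625) = 5.2%

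**All cases, tau known, delta_0 fixed.** The exchangeable model gives 2.5% in each by construction.

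| S | tau 0.1 | 0.2 | 0.3 | 0.4 |
|---|---|---|---|---|
| 2 | 3.3% | 4.3% | 4.6% | 4.5% |
| 3 | 3.5% | 5.2% | 6.0% | 6.0% |
| 5 | 3.9% | 6.5% | 8.3% | 8.9% |

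**Tau estimated (simulation, 20,000 runs per cell).** With a half-normal prior of scale 0.5 on the log-rate scale and 75 boys per source, the fixed model gives 2.1% to 3.4% (S = 2), 2.2% to 4.2% (S = 3) and 2.8% to 6.0% (S = 5). A second set on the points scale, with prior scales of 0.3 to 1.5 points, gives 2.2% to 8.3% fixed against 1.8% to 4.4% exchangeable. In that set the five-source cells all exceed 2.5%. With two sources and the most diffuse prior, error is 2.2% to 2.5%. The 8.3% comes from S = 5 and a prior scale of 0.3 points when the true tau is 0.6 points.

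**Fixed adverse drift (S = 3, 100 boys per source, tau = 0.2, known).** If historical boys decline faster by 1 SD (0.6 points), error is 10.5% fixed v 4.4% exchangeable. At 2 SD it is 29.4% v 10.1%.

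These are normal approximations to a nonlinear model, so the sizes are indicative.

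**The case against.** The strongest reply is that delta_0 = 0 is by itself only a reference constraint. Because beta_k is defined as this study's placebo decline, some source has to be the baseline. Everything then depends on the distribution of the historical effects, which the section leaves open. If they have variance 2tau² and covariance tau², their mean has variance (2tau² + (S − 1)tau²)/S = tau²(1 + 1/S), which is the exchangeable model written as contrasts against this trial. That stands, and it makes the point conditional. Nothing in the section states such a covariance, however, and independent zero-mean effects are what the term random effect ordinarily means. A free mean with a vague prior would leave little borrowing, against the stated aim.

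A reader might infer that the 2.5% error rate is not protected. The documents do not support that. Tau, S, the source sizes and the prior are all absent, and some plausible settings stay at about 2.5%. Section 11.3.3 asserts simulated control directly after naming both the dystrophin and the NSAA analyses, and the 0.975 rule has no regional variant, so the simulations should not be read as leaving NSAA out. The fair criticism is that no scenario is listed, so drift between sources may or may not have been covered.

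A reader might also take the limit of very large sources as the size of the problem. At S = 3 and tau = 0.2 that gives 2.25/(0.04/3) = 169 placebo-equivalents and 6.65% error. With 75 boys per source the figures are 96 and 5.2%.

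Baseline covariates are in the model, so tau is residual heterogeneity and could be small. The covariate list is not given, so this can be neither relied on nor dismissed.

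**Conclusion.** The concern holds conditionally. The text fixes this trial's source effect and makes only the historical ones random. If those are independent with mean zero, the trial is placed at the centre of the source distribution and historical controls count for more than an exchangeable model would allow: about 96 against 36 placebo-equivalents at S = 3, tau = 0.2 and 75 boys per source.

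Under the stated assumptions, average one-sided error runs from 3.3% to 8.9% with tau known and from about 2% to 8% with tau estimated. The low end belongs to few sources and a diffuse prior. The conclusion is that the control promised in Section 11.3.3 is not shown to hold under between-source drift. It is not that control has been shown to fail. Because this is a primary analysis in one regional strategy and a key secondary in the other, the model should be settled before any unblinded NSAA analysis.

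**What to change.** In Section 11.3.2.2 and the SAP, replace delta_0 = 0 with delta_0, delta_1, ..., delta_S all drawn from N(0, tau²). Define beta_k at the mean of the source distribution, and report this trial's placebo decline as exp(delta_0) times the sum of the beta_k. Equivalently, keep delta_0 = 0 and give the historical contrasts variance 2tau² and covariance tau². In either form:
- state the prior on tau, since the results depend on it, and name the historical sources;
- use the same model for the NSAA interim predictive probability;
- report NSAA type I error with the trial's own effect drawn from N(0, tau²), and under fixed adverse drift, for both regional strategies.

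If the SAP already specifies the correlated form, say so in the protocol and add the drift scenarios.

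The cost is a short text change, including the redefinition of beta_k, and a rerun of the simulations. Less is borrowed, so the DRR interval will be somewhat wider. The stated 88% power uses no historical data and is unaffected. The change lessens the inflation from adverse drift but does not remove it, which is why the drift scenarios are needed as well.

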4.1.4 Discontinuation and Withdrawal

Patients who discontinue study treatment prior to study completion, will be encouraged to remain in the study to be monitored and to complete all study related procedures until study completion.

Patients withdrawing from the study will be requested to come back to the clinic for an early termination (ET) visit ([Table 1](#) [ET visit for double-blind period] and [Table 2](#) [ET visit for OL period]) to have relevant safety and efficacy assessments performed.

Any patient, for whom consent to participate in the study is withdrawn, will be removed from further treatment and study observation immediately upon the date of request.

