5.4.2 Discontinuation of Study Treatment

A patient may permanently discontinue study treatment for any of the following:

- The patient is withdrawn from the study ([Section 5.4.1](#)).
- The patient experiences a serious or intolerable AE that in the Investigator's opinion requires treatment discontinuation (*e.g., severe or serious reactions during infusion, such as hypotension requiring treatment, dyspnoea requiring bronchodilators, angioedema or generalized urticaria require immediate discontinuation of the study drug administration, aggressive symptomatic therapy, and the patient should not be re-challenged.*).
- A change in the patient's medical condition not consistent with the protocol requirements or that justifies withdrawal from the study or study drug.

If a patient discontinues treatment, they will be encouraged to remain in the study to be monitored and to complete all study related procedures, unless consent is withdrawn. Patients who discontinue treatment due to an AE ([Section 9](#)) may require longer follow-up.

The reason for discontinuation of study treatment must be recorded in the eCRF and source documentation.

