6.2.4.2 Monitoring for Thrombocytopenia and Criteria for Withholding Study Drug

Patients will be closely monitored for thrombocytopenia. Prior to each dose, samples for assessments of platelets will be collected and analyzed locally. Abnormal results should be repeated locally for confirmation. Concurrent samples should also be collected and sent to the central laboratory for analysis. Local results should be reviewed against the following criteria:

- If platelet values fall to <100,000 platelets/ μ L and the patient has new clinical signs or symptoms indicative of thrombocytopenia, drug will be held. Dosing can resume when symptoms have resolved and platelets are >150,000 platelets/ μ L.
- If platelet values fall to <50,000 platelets/ μ L, drug administration will be discontinued and the patient will be followed until resolution.
- If a platelet measurement is uninterpretable, a repeat platelet count should be obtained as soon as possible using a sodium citrate tube.
- **Note:** For patients who experience a decrease in platelets to <75,000 platelets/ μ L, an antiplatelet antibody test should be performed. If the result is indeterminate, the test should be repeated. In the case that the anti-platelet antibody test is positive, a repeat test should be performed at end of treatment.

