Summaries of the posterior distribution for the treatment difference in dystrophin compared to placebo at each time point for each arm will be provided including the probability that each treatment is superior to placebo at each time point, $\Pr(\theta_{T,j} > 0)$, as well as mean and 95% credible intervals.

The dystrophin analysis will be supplemented with dystrophin data from the ongoing Open-label extension study to the Phase 1 trial (WVE-DMDX51-002). These results will be available at the time of the first dystrophin interim analysis.

Missing dystrophin data can result from intercurrent events which include discontinuation of the study and non-evaluable biopsies. Previous pivotal studies in DMD, including exon skipping therapies, have had low study discontinuation rates (e.g. 0.6% and 2.7%) so it is anticipated that missing data resulting from study discontinuation will be limited (^{57,58}). With the selected estimand, missing dystrophin results due to study discontinuation will be handled using baseline imputation. Non-evaluable dystrophin will be addressed using imputation under the assumption of missing-at-random (MAR). The regression method for monotone missing data will be used for the multiple imputation with baseline dystrophin as a covariate and imputation stratified by treatment arm.

There will be two interim dystrophin efficacy analyses and a final dystrophin efficacy analysis. The dystrophin treatment effects will be declared significant at the interim or final analyses using a gatekeeping strategy where the WVE-210201 4.5 mg/kg arm is assessed first and, if significant, the WVE-210201 3 mg/kg arm is assessed. To account for the three possible analyses of the dystrophin treatment effects, a Bonferroni-level adjustment will be applied. A one-sided, significance threshold of $1 - (0.025/3) = 0.991667$ will be used for the Bayesian posterior probability of superiority of each dose compared to placebo. If successful for WVE-

210210 4.5 mg/kg, the same threshold will be used for WVE-210210 3 mg/kg. Specifically, success will be declared for WVE-210201 4.5 mg/kg if

1. $\Pr(\theta_{2,1} > 0) > 0.991667$ at the first dystrophin interim analysis,
2. $\Pr(\theta_{2,2} > 0) > 0.991667$ at the second dystrophin interim analysis, or
3. $\Pr(\theta_{2,3} > 0) > 0.991667$ at the final dystrophin analysis.

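### The NSAA analysis names a treatment-policy estimand but replaces active-arm scores observed after treatment discontinuation with control-based imputations, so estimator and estimand do not match

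*Combined protocol and SAP*

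**What the plan says.** For NSAA, Section 11.3.2.2 states: "The treatment policy estimand which assesses the effect of treatment initially assigned at baseline (regardless of adherence to the planned course of treatment"; the population is ITT. Later in that section, the missing-data paragraph presents its handling as following from that estimand and says that "missing NSAA assessments or NSAA assessments collected after randomized therapy discontinuation will be imputed using a control-based imputation strategy for treated patients". For the other arm it says only: "Placebo patients will have missing observations imputed assuming MAR".

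Off-drug scores are meant to be collected. Under Section 4.1.4, patients who stop treatment "will be encouraged to remain in the study to be monitored and to complete all study related procedures until study completion". Section 5.4.2 repeats this: "If a patient discontinues treatment, they will be encouraged to remain in the study to be monitored". Stopping drug while remaining under observation is also foreseen in the safety rules; at the lowest platelet threshold in Section 6.2.4.2, "drug administration will be discontinued and the patient will be followed until resolution".

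Section 11.3.2.1 names the same estimand for dystrophin but imputes only results that do not exist or cannot be read: "missing dystrophin results due to study discontinuation will be handled using baseline imputation", and non-evaluable biopsies are imputed under missing-at-random (MAR).

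**The concern.** Under a treatment-policy strategy, stopping drug does not change which outcome is of interest: the score recorded afterwards is the outcome. Replacing it with a control-like value targets a different quantity, roughly the effect if patients reverted to the control course on stopping. The plan makes this the primary handling, not a sensitivity analysis.

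The arms also appear to be treated differently, because nothing in the placebo sentence removes observed off-drug scores.

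At stake is the meaning of the DRR on which the NSAA claim rests (success if the posterior probability that DRR < 1 exceeds 0.975). If boys who stop keep part of their benefit, the rule shrinks the effect. If they stop for toxicity and then decline faster than placebo, the rule removes their poor scores and flatters the drug. The two estimands agree only if stoppers follow the imputed course.

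**Working it through.** The mismatch is textual. The arithmetic shows only how large it could be.

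**Inputs (Section 11.1).** Difference 3.0 points, SD 4.5, two-sided 5%, 150 patients at 1:1:2:2, 10% dropout. Pooled placebo is 50, and each dose is 50; after dropout, 45 each. Section 11.3.2.1 cites study discontinuation of 0.6% and 2.7% in earlier pivotal trials. No rate of treatment discontinuation is given.

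**The plan's own figure.** Two-sample t-test power (noncentral t):
- One dose v pooled placebo, 45 v 45: SE = 4.5 × √(1/45 + 1/45) = 0.95; power 87.9%. This reproduces the stated 88%.
- Both doses pooled v pooled placebo, 90 v 45: SE = 4.5 × √(1/90 + 1/45) = 0.82; power 95.2%. This is the default NSAA comparison, since Section 11.3.2.2 pools the doses unless randomization to 3 mg/kg stops.

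**Shift in the Week 48 difference.** Let p be the fraction of active patients who stop drug but still have a Week 48 score, and g the gap between their true mean and the imputed control mean. Then shift = p × g. Taking g = 3.0 (full benefit retained) as the bound:

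| p | Shift, g = 1.5 | Shift, g = 3.0 | Difference under the rule, g = 3.0 | Power 90 v 45 | Power 45 v 45 |
|---|---|---|---|---|---|
| 0 | 0 | 0 | 3.00 | 95.2% | 87.9% |
| 0.6% | 0.009 | 0.018 | 2.98 | 95.0% | 87.5% |
| 2.7% | 0.041 | 0.081 | 2.92 | 94.1% | 86.1% |
| 10% (assumed) | 0.15 | 0.30 | 2.70 | 90.4% | 80.4% |

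The power columns use g = 3.0. In the other direction, if stoppers end 1.5 points worse than placebo at p = 10%, the treatment-policy difference is 3.0 × 0.9 − 1.5 × 0.1 = 2.55, while the rule gives 2.70: an overstatement of 0.15 points.

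**DRR scale.** Take the section's example DRR of 0.75, a linear placebo decline over four visits, stopping spread evenly after visits 0 to 3, and a least-squares proportional fit. The fitted DRR is Σ j·m(j) / Σ j², where m(j) is the mean decline at visit j in units of one placebo increment and Σ j² = 30.
- *Imputed with placebo increments after stopping.* A stopper after visit s adds 0.25 × Σ j(j − s)/30 over j > s. The sums for s = 0 to 3 are 30, 20, 11 and 4, mean 16.25. Reported DRR = 0.75 + p × 0.25 × 16.25/30 = 0.754 (2.7%) or 0.764 (10%).
- *Imputed by a jump to the placebo mean.* The sums are 30, 29, 25 and 16, mean 25. Reported DRR = 0.75 + p × 0.25 × 25/30 = 0.756 or 0.771.
- *Treatment-policy DRR, benefit retained:* 0.750.
- *Treatment-policy DRR, off-drug decline at twice the placebo rate:* 0.75 + p × 1.25 × 16.25/30 = 0.768 or 0.818.

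At 10% stopping, the rule reports 0.764 to 0.771 whether the treatment-policy value is 0.750 or 0.818. The off-drug scores that would tell these cases apart have been removed. All figures ignore historical borrowing and patient random effects.

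**The case against.** The strongest reply is that the effect is small at the only observed rates. At 2.7% the bounding shift of 0.08 points is about a tenth of a standard error (0.82 to 0.95), and those rates are for leaving the study, not stopping drug. The visible effects need an assumed 10% who stop and still attend; the protocol's own 10% is dropout, whose scores are mostly missing and outside this point. The bounding shift also charges every stopper the full 3-point gap. With stopping spread over visits 0 to 3 and placebo increments imputed, the 10% shift is 0.10 × 3.0 × 0.625 = 0.19 points, with power about 92.5% (90 v 45) or 83.5% (45 v 45). The point-scale and DRR illustrations rest on different effect sizes and should not be combined. All of this stands as to size.

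It can also be said that control-based imputation is conservative. It is when benefit is retained, and with no drug effect on or off treatment it creates no mean difference. It is not conservative when stoppers do worse than placebo. The documents give no evidence for a doubled off-drug decline; it is only an illustration.

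The retention of observed off-drug placebo scores is inferred from silence. That is fair, and the silence itself needs filling. The platelet rule concerns follow-up of the event, not NSAA; the support for off-drug NSAA data is Sections 4.1.4 and 5.4.2, where patients are only encouraged to stay. Finally, Section 11.5 refers to a SAP for thresholds and targets, and details may be there; but nothing in the supplied text reconciles the two statements, and the protocol wording would still need correcting. None of these replies removes the contradiction.

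**Conclusion.** The concern holds and should be fixed. The primary NSAA handling does not estimate the treatment-policy effect that the same section names, and on a literal reading it treats the arms differently. Control-based imputation of scores that are truly missing can be compatible with the estimand; the defect is confined to scores that were observed.

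The likely size is small if stopping drug is as rare as the cited study discontinuation (at most about 0.08 points, and about one percentage point of pooled-dose power). It would matter at an assumed 10% (up to 0.30 points, with pooled-dose power 90.4% instead of 95.2%). Direction is not known in advance. These sizes rest on assumed stopping rates, assumed off-drug courses and a simple t-test or least-squares approximation to the Bayesian model. The mismatch itself rests on the text alone.

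**What to change.** In Section 11.3.2.2 and the SAP:
- Use every observed NSAA score in all arms, whether or not treatment has been discontinued.
- Limit control-based imputation (active) and MAR imputation (placebo) to scores that are truly missing, and name the type of control-based imputation.
- Keep the present replacement rule as a sensitivity analysis.
- State whether patients moved off the 3 mg/kg arm under Section 11.5.1 count as having discontinued randomized therapy. That section already leaves them out of the 4.5 mg/kg clinical effect estimate.

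The alternative is to keep the rule, rename the estimand to match it, and apply one stated rule for post-discontinuation scores to every arm. That gives up the effect regardless of adherence, so it is second best.

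The cost is a wording change made by amendment, with no new data collection, since Sections 4.1.4 and 5.4.2 already plan the visits. The same data rule must be carried into the four NSAA interim predictive-probability calculations (Section 11.5.2) and any affected simulations behind the type I error statement in Section 11.3.3, plus one additional sensitivity analysis.
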